Secondary endpoints will be serum markers of ovulation (estradiol [E₂], progesterone [P], follicle stimulating hormone [FSH], and luteinizing hormone [LH]), as well as evidence of ovulation on cervical mucus exam and transvaginal ultrasound (presence and subsequent disappearance of a dominant follicle >15 mm diameter)[19]. Blood for hormone assays will be drawn at the Bayview CRU at the same time as samples for ENG and EFV. During these visits participants will also undergo a pelvic exam for cervical mucus assessment, and a pelvic ultrasound to look for ovarian follicular activity. Monitoring throughout the study will allow us to compare ovarian activity across time points through both ultrasound visualization and ovarian hormone testing (E₂ and P). Changes in cervical mucus quality secondary to the progestin activity of ENG provide secondary contraceptive effects that may be maintained even if ovulation occurs. Continued monitoring for several weeks after cessation of EFV will allow us to follow subjects for the equivalent of a normal menstrual cycle, to ascertain whether either contraceptive effect (ovulation suppression or cervical mucus quality) was altered. Urine pregnancy tests may be repeated throughout the duration of the study as needed.

Ultrasounds and venipuncture for LH, FSH, E₂ and P levels will occur in the CRU. A total of 20 mL of venous blood will be collected for each outpatient visit. FSH, LH, E₂, and P assays will be performed by the CRU at JHU. FSH and LH will be measured using the automated immunoradiometric assay (IRMA) system. Assay sensitivity of LH assays is 0.07 mIU/ml; assay sensitivity of FSH assays is 0.2 mIU/ml. P will be measured using an automated immulite chemiluminescent assay system. Assay sensitivity of the P assay is 0.05 ng/ml. E₂ will be measured via an ultra-sensitive competitive binding radioimmunoassay with sensitivity of 2.2 pg/ml. The EFV assay will be performed through the Johns Hopkins Hospital Clinical Pharmacology Analytical Lab, and will be measured via LC-MS/MS assay with a lower limit of quantification of 0.5 ng/ml.

An assay for ENG is not commercially available, but the Irving Institute for Clinical and Translational Research at the Columbia University Medical Center in New York has developed a validated assay. ENG concentrations will be measured by LC-MS/MS, and the assay has a lower limit of quantification of 50 pg/ml.

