- She becomes pregnant
- She experiences a serious adverse event
- She requests to stop the study

g. Description of what happens to participants receiving therapy when study ends or if a participant's participation in the study ends prematurely.

If a participant leaves the study prior to its completion, there will be no effect on her general medical care. At the conclusion of the study, participants will not receive any additional study medications and will return to their routine care providers for ongoing care as needed.

5. Inclusion/Exclusion Criteria

Inclusion Criteria:

- Healthy women aged 18-40 years who have a Nexplanon®/Implanon® in place that is palpable on exam, had the device placed between 12 and 24 months prior to enrollment, and can provide documentation of when the implant was placed
- Able to speak and read English
- Documented HIV-negative status within 30 days of enrollment
- BMI between 18.5 and 29.9 kg/m²
- Willingness to take a two-week course of reduced-dose efavirenz
- Willingness to comply with study visit schedule (as described below), including blood sampling, transvaginal ultrasounds, and cervical mucus assessment
- Negative urine hCG pregnancy test at study entry
- Normal laboratory values within 30 days of study entry, as specified below:
 - o White blood cell count ≥ 4500 and ≤ 11000 cells/mm³
 - o Platelet count $\geq 100,000$ platelets/mm³

Date: January 5th, 2017

Principal Investigator: [name], MPH

Application Number: NA_00087585

- Hemoglobin \geq 8.0 g/dL
 - International normalized ratio (INR) \leq 1.8
 - Aspartate transaminase (SGOT) and alanine aminotransferase (SGPT) \leq 3 times the upper limit of normal (ULN) (upper limit of normal)
 - Creatinine \leq 1.5 x ULN
 - Serum amylase \leq 1.5 x ULN
 - Total bilirubin \leq 2.0 x ULN
- Agree to use an additional reliable method of contraception while participating in the study.
Acceptable methods include:
 - Abstinence
 - Condoms (male or female) with or without spermicide
 - Pre-existing sterilization of subject or her male partner
- Willingness to abstain from alcohol consumption during the study period
- Willingness to abstain from any grapefruit product or supplement for the duration of the study.

Exclusion Criteria:

- Breastfeeding
- Hypersensitivity to efavirenz
- History of seizure disorder
- History of significant psychiatric illness
- Initiated, discontinued, or changed doses of drugs that are CYP3A4 inducers or inhibitors within 30 days of study entry.

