EFV was chosen for this study because it is the backbone of one of the preferred antiretroviral regimens recommended by the NIH[24]. As such, it is commonly taken by women of reproductive age. There is some concern that EFV increases the risk of neural-tube defects when exposure occurs during the first 5-6 weeks of pregnancy[21]. For this reason, it is particularly important to avoid unintended pregnancy in women taking EFV. Determining whether the ENG implant retains its high level of contraceptive efficacy in women taking EFV is important so that HIV-positive women and their healthcare providers can make the most informed decisions regarding antiretroviral regimens and contraception.

The dose of EFV that is used in clinical practice is 600 mg given orally once per day, typically at bedtime, and it is generally well tolerated[25]. Recent data suggest that a lower daily dose of EFV (400 mg) is as effective as the standard 600 mg dose in suppressing HIV, with lower incidence of drug-related side effects. As the criteria for starting ART continue to broaden, there is considerable concern about the costs of providing treatment to more individuals, and reducing the accepted dose of EFV is one strategy to make ART available to as many people as possible[26].

Certain drugs are contraindicated or not recommended for use with EFV, including ergot derivatives, benzodiazepines, calcium channel blockers, cisapride, pimozide, and St. John's wort. Women taking these drugs will be excluded from the study due to potential adverse drug interactions. While the 400 mg daily dose of EFV has been associated with a lower incidence of drug-related adverse events, participants will be informed of potential adverse reactions to EFV prior to enrolling in the study, and will be counseled regarding when and how to inform study personnel of any potential adverse reactions. The adverse reactions that have been identified in studies comparing EFV-based antiretroviral regimens to control regimens include:

- Psychiatric symptoms: depression (19% with EFV-based regimen vs. 16% with control), anxiety (13% vs. 9%), nervousness (7% vs. 2%)

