Given that co-administration of EFV with the ENG implant may lead to decreased serum concentrations of ENG, participants may experience greater or lesser breakthrough bleeding than is typical with the ENG implant. They could also experience an improvement in progestin-related side effects with lower ENG concentrations.

Unintended Pregnancy

Since the goal of the study is to determine whether reduced-dose EFV lowers the serum concentration of ENG to a level where ovulation might occur, there is the possibility that a participant could ovulate during

Date: January 5th, 2017

Principal Investigator: [name], MPH

Application Number: NA_00087585

or after taking reduced-dose efavirenz. If she is sexually active during the study, this would put her at risk of an unintended pregnancy. There is also some concern that EFV may cause neural tube defects when taken during the first trimester. This risk was suggested by isolated case reports; however, larger reviews have found no increased risk in congenital anomalies with EFV.

b. Steps taken to minimize the risks.

Participants will be advised to take EFV at bedtime and on an empty stomach in an effort to minimize the central nervous system effects. They will also be counseled about the potential for psychiatric effects and rash as part of the informed consent process, and will be provided with contact information for study personnel should they experience any concerning symptoms. If needed, depending on the nature of the psychiatric symptoms or effects, participants will be referred for appropriate clinical care. This may include the emergency department, a psychologist, or the participant's primary care physician.

Participants will also be encouraged to either abstain from intercourse during the study period, or to use an additional backup method such as male or female condoms. They will be counseled about the potential for unintended pregnancy and teratogenic effects as part of the informed consent process. Participants will also be counseled about the availability of emergency contraception (either over-the-counter or by prescription) if they ever feel at risk for unintended pregnancy during the study (i.e. in the event of condom breakage).

c. Plan for reporting unanticipated problems or study deviations.

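### Backup contraception is tied to study participation, not to the last efavirenz dose, so the protocol does not ask a woman who leaves early to continue it (minor participant-safety point)

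*Combined protocol and SAP*

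**What the plan says.** All references are to the combined protocol and SAP.

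- **Section 5, inclusion criteria.** A woman must "Agree to use an additional reliable method of contraception while participating in the study". Abstinence, condoms and pre-existing sterilization are acceptable.
- **Section 8b, minimizing risks.** The wording is softer: "Participants will also be encouraged to either abstain from intercourse during the study period", or to use a backup method such as condoms. On counselling: "They will be counseled about the potential for unintended pregnancy and teratogenic effects as part of the informed consent process". Also: "Participants will also be counseled about the availability of emergency contraception".
- **Section 8a, unintended pregnancy.** A participant could ovulate during "or after taking reduced-dose efavirenz. If she is sexually active during the study, this would put her at risk of an unintended pregnancy". Contraceptive failure is one of the two categories of medical risk that 8a names.
- **Section 4a, follow-up.** "Continued monitoring for several weeks after cessation of EFV will allow us to follow subjects for the equivalent of a normal menstrual cycle". The purpose is to see whether ovulation suppression or cervical mucus was altered.
- **Section 4a, Table 1.** Urine pregnancy tests are scheduled at Screening and Day 42 only. The text of 4a allows further tests as needed while the study lasts.
- **Sections 4f and 7d.** Exit routes include missing more than three visits, a serious adverse event, the woman's own request, a request for implant removal and use of emergency contraception.
- **Section 4g.** Leaving early does not affect general medical care. Nothing is said about contraception or a pregnancy test at exit.

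**The concern.** Any loss of implant effect follows from exposure to EFV, not from enrolment. The protocol accepts that this effect could outlast dosing, since it names ovulation after EFV as possible and follows women for 4 weeks afterwards. Yet the Section 5 rule ends when participation ends. A completer is covered for those 4 weeks; a woman who took the same EFV course and left at Week 2 is not asked to do anything further.

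Two exit routes in 7d make the gap concrete. A woman may be removed after taking emergency contraception, when she has just felt at risk of pregnancy. A woman who asks for implant removal may also be removed from the study, and then loses the implant as well.

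What is at stake is participant safety on a small scale: backup contraception is the main step that 8b sets against contraceptive failure.

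**Working it through.** **Inputs.** Section 4b: 2 weeks on EFV and 4 more weeks of follow-up. Section 4a: 14 nightly doses starting on the evening of Day 1, so the last planned dose is the night of Day 14; visit window +/- 1 day. Table 1: visit days and the pregnancy-test row.

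**The plan's own figures.** Day 42 − Day 14 = 28 days = 4 weeks, as stated. Visits from Day 1 on are Days 1, 2, 7, 11, 14, 18, 21, 25, 28, 32, 35, 39 and 42, which is 13; with Screening, 14, as stated.

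**Reference period.** The protocol gives no EFV washout or enzyme-recovery time and defines no at-risk window. The 28 days below are borrowed from its follow-up. They may be longer or shorter than the true period of altered implant effect.

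**Follow-up days without stated backup** = max(0, day of last EFV dose + 28 − exit day).

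| Last dose | Exit | Calculation | Days |
|---|---|---|---|
| Day 14 | Day 14 | 14 + 28 − 14 | 28 |
| Day 13 | Day 14 | 13 + 28 − 14 | 27 |
| Day 14 | Day 21 | 14 + 28 − 21 | 21 |
| Day 14 | Day 28 | 14 + 28 − 28 | 14 |
| Day 14 | Day 35 | 14 + 28 − 35 | 7 |
| Day 14 | Day 39 | 14 + 28 − 39 | 3 |
| Day 7 | Day 28 | 7 + 28 − 28 | 7 |
| Day 14 | Day 42 (completer) | 14 + 28 − 42 | 0 |

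The Day 13 row is a woman who leaves on Day 14 having taken her last dose the night before. A completer seen on Day 41 under the visit window has 14 + 28 − 41 = 1 day.

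These are maxima. They assume that she stops backup on the day she leaves, and a woman relying on abstinence or sterilization may not be affected at all.

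**Visits and tests forgone.** A woman who leaves after the Day 14 visit misses Days 18, 21, 25, 28, 32, 35, 39 and 42, which is 8 of the 13, including the Day 42 pregnancy test.

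**Number of women.** Not computable. Section 7c allows for 20% drop-out, but this is a planning figure with no timing, and it does not separate women who leave before any EFV from those who leave after.

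**The case against.** The strongest objection is that the consent pages are not in the file. Section 8b places counselling on pregnancy and teratogenic effects in the consent process, and advice on leaving early may sit there too. This stands as a limit: the point shows only that the protocol text does not give the advice. It does not correct the anchor in Section 5.

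Second, the period named in 8b could mean the fixed six weeks of 4b. An early leaver would then already have been encouraged to use backup to Day 42. That reading is open, but 8b would then differ from Section 5, and the two should be aligned.

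Third, existing cover is real. The implant stays in place except on the removal route, mucus effects may persist even if ovulation occurs, general care continues, and emergency contraception is discussed. As-needed testing already permits a pregnancy test at the last attended visit. All of this stands and keeps the point minor.

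A reader might also infer a teratogenicity argument, because Section 6 says "it is particularly important to avoid unintended pregnancy in women taking EFV". That sentence concerns women taking EFV and exposure early in pregnancy, whereas the gap concerns women who have stopped. The documents give no residual-exposure figure to connect the two, and 8a adds that "larger reviews have found no increased risk in congenital anomalies with EFV". The rationale here is possible reduced implant effect after EFV, not neural-tube risk.

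**Conclusion.** The point holds as a cheap, optional improvement. Section 5 states a backup rule with the wrong anchor, and 4g does not repair it for a woman who leaves early after taking EFV. Against the protocol's own 4-week follow-up, the shortfall is 28 calendar days at most with a Day 14 exit and falls to 0 for a completer seen on Day 42.

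This rests on the Section 5 wording being the operative rule, on 28 days as a borrowed reference, and on the consent form not already giving the advice.

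Three stronger readings are not supported. A reader might infer that an early leaver is unprotected, or at quantified risk, for up to 28 days; the counts are calendar days, and she normally still has the implant. A reader might infer that she cannot be tested; only the scheduled test is lost. A reader might turn the 20% allowance into a number of exposed women; its timing is not given. Completers (apart from the one-day window case), sample size and the pharmacokinetic analysis are unaffected.

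**What to change.** 1. In Sections 5 and 8b, set the backup period to run until at least 4 weeks after the last EFV dose, whether or not the woman stays in the study. Because Section 5 is an entry agreement, every woman would hear this before her first dose, including one who later stops attending.
2. In 4g, state that a woman who leaves early after any EFV dose, including by removal under 4f or 7d, is advised of that date and is offered the final-visit urine pregnancy test at exit if she attends.
3. Align the consent form if it does not already say this.

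The cost is protocol and consent wording plus one urine test per early leaver who attends. No later call or second test is needed. The limits are plain: the advice cannot be enforced after withdrawal, an exit test cannot detect a later conception, and a woman removed for missed visits may not come for it.

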This will be a prospective, single arm pilot pharmacokinetic (PK) study. We will recruit 18 healthy, HIV-negative women aged 18 to 40 years who are using Nexplanon®/Implanon® for contraception and who are willing to take a reduced dose of EFV for 2 weeks. We will limit enrollment to women who have had the ENG implant in place 12 to 24 months to avoid the initial burst release of ENG after implant placement, and to target the time frame of concern based on case studies of contraceptive failures among women on HAART. Performing the study in women without HIV infection will allow us to evaluate any interactions between ENG and EFV without having to contend with the effects of other drugs that make up typical HAART regimens. A two-week course of EFV will be sufficient for EFV to reach steady-state concentration while minimizing exposure in these healthy volunteers. By using the reduced dose of EFV (400 mg daily instead of the standard 600 mg daily dose)

Over 6 weeks from study entry, we will perform twice-weekly (see visit schedule) quantitative assessments of serum ENG as well as serum hormone concentration analysis, pelvic ultrasound for markers of ovulation, and cervical mucus testing, as described below. Given the slow apparent clearance of ENG and based on previous PK studies, we estimate that sparse sampling will be adequate to assess changes in ENG clearance during EFV administration. EFV will be administered for 14 days from the beginning of the study, after collection of baseline samples for ENG concentration determination. All study procedures will take place at the Johns Hopkins Bayview Medical Center's Clinical Research Unit (CRU). All blood tests will be performed locally except for ENG concentrations, which will be performed at Columbia University

Date: January 5th, 2017

Principal Investigator: [name], MPH

Application Number: NA_00087585

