Data collection: After successful screening, women will be asked to take 14 days of EFV in a once-nightly 400 mg regimen. We will collect blood samples for baseline ENG concentration on the day participants begin taking EFV, before the first dose (Day 1, times 0 hour, 1 hour, and 2 hours). The first dose of EFV will be taken in the evening of Day 1, and the next blood sample for ENG concentration will be drawn twelve to twenty hours after the first dose of EFV. (For example, if a participant takes her first dose of EFV at 10 PM on Day 1, she will be asked to return to the CRU between 10 AM and 6 PM on Day 2.) We will then obtain subsequent samples every 3 to 4 days (+/- 1 day) for the remainder of the two week EFV course and for 4 additional weeks (through Week 6 of study participation). This is a total of 14 outpatient visits, including screening. All serum samples will be analyzed for concentrations of ENG, which will be used to derive the ENG area under the concentration-time curve (AUC), the maximum and minimum observed serum drug concentration (C_{max}, C_{min}), and the apparent average serum concentration at steady-state (C_{ss,avg}) using WinNonlin®. EFV concentrations will be determined from plasma samples obtained at 2 timepoints during EFV administration, and measured using a validated LC/MS/MS assay in the Clinical Pharmacology Analytical Laboratory of the Johns Hopkins Hospital.

Table 1: Participant Visit Schedule and Timing of Study Assessments

Visit	Screening	Study Entry			Week 1		Week 2		Week 3		Week 4		Week 5		Week 6	
		1			2	7	11	14	18	21	25	28	32	35	39	42
Serum Tests		0 hr	1 hr	2 hr												
ENG		X	X	X	X	X	X	X	X	X	X	X	X	X	X	X
EFV					X			X								
FSH		X			X	X	X	X	X	X	X	X	X	X	X	X
LH		X			X	X	X	X	X	X	X	X	X	X	X	X
Estradiol		X			X	X	X	X	X	X	X	X	X	X	X	X
Progesterone		X			X	X	X	X	X	X	X	X	X	X	X	X
Safety Labs	X															X
UPT	X															X
HIV	X															X
TVUS	X				X	X	X	X	X	X	X	X	X	X	X	X
CM	X				X	X	X	X	X	X	X	X	X	X	X	X

Date: January 5th, 2017

Principal Investigator: [name], MPH

Application Number: NA_00087585

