- Nervous system symptoms: dizziness, insomnia, impaired concentration, somnolence, abnormal dreaming, euphoria, confusion, agitation, amnesia, hallucinations, stupor, abnormal thinking, depersonalization. Mild symptoms occurred in 33.3% of patients taking EFV compared to 15.6% of patients in control groups; moderate symptoms occurred in 17.4% of patients taking EFV compared to 7.7% of controls; and severe symptoms occurred in 2% of patients taking EFV compared to 1.3% of controls.
- Rash: 26% of patients taking EFV developed a rash compared to 17% of patients in control groups. A grade 4 rash (erythema multiforme, Stevens-Johnson syndrome, toxic epidermal necrolysis, necrosis requiring surgery, exfoliative dermatitis) was seen in 0.1% of patients treated with EFV and no patients in control groups. Rashes usually occur during the first two weeks of treatment, and are mild-to-moderate maculopapular skin eruptions. The rash typically resolves within one month in patients who continue EFV.
- Hepatotoxicity: it is recommended that liver enzymes be evaluated before and during treatment with EFV, as EFV can cause elevated liver enzymes even in patients without underlying hepatic disease.
- Convulsions: Convulsions have been noted in patients treated with EFV, typically in the setting of a known seizure disorder.
- Lipid elevations: EFV can lead to increased concentrations of total cholesterol and triglycerides. Some HIV-uninfected volunteers who received EFV were noted to have 10-20% increases in total cholesterol from baseline.

Date: January 5th, 2017

Principal Investigator: [name], MPH

Application Number: NA_00087585

- **Fat redistribution:** Body fat may redistribute or accumulate in certain regions of the body, including central obesity, dorsocervical fat enlargement (buffalo hump), peripheral wasting, facial wasting, breast enlargement, and “cushingoid appearance.” This phenomenon has been noted among patients taking antiretroviral therapy in general, and while it has not been specifically linked to EFV, it is a potential adverse reaction to this drug.
- c. Justification and safety information if non-FDA approved drugs without an IND will be administered.

Not applicable

7. Study Statistics

- a. Primary outcome variable.

Primary Outcome: Serum concentrations of ENG before and after two weeks of reduced-dose EFV

- b. Secondary outcome variables.

Secondary Outcomes:

- Serum concentrations of EFV at the start and end of the study period

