d. Early stopping rules.

Participants may be removed from the study under the following circumstances:

- Participant requests to withdraw from the study
- Participant requests that she have the ENG implant removed prior to conclusion of the study. (Of note, removal would be performed by the subject's clinician and not performed as part of the study.)
- Participant judged by the investigator to be at significant risk of failing to comply with the provisions of the protocol as to cause harm to self or seriously interfere with the validity of the study results.
- Participant takes emergency contraception during the study

8. Risks

a. Medical risks, listing all procedures, their major and minor risks and expected frequency.

The medical risks related to participation in this study fall into two categories: medication side effects or adverse reactions, and possible contraceptive failure.

Medication Adverse Reactions:

The most common adverse reactions for EFV are:

- Psychiatric symptoms – severe depression (2.4%), suicidal ideation (0.7%), nonfatal suicide attempts (0.5%), aggressive behavior (0.4%), paranoid reactions (0.4%), and manic reactions (0.2%)
- Central nervous system symptoms (overall incidence 53%) – dizziness (28.1%), insomnia (16.3%), impaired concentration (8.3%), somnolence (7%), abnormal dreams (6.2%), and hallucinations (1.2%) (usually begin during the first 2 days of therapy and resolve after 2-4 weeks).
- Rash (26%) – usually mild to moderate maculopapular skin eruptions that occur within the first 2 weeks of initiating therapy and typically resolve within 1 month

Additional adverse reactions to EFV include elevated liver enzymes, convulsions, elevated total cholesterol and triglycerides, and fat redistribution. Adverse reactions attributed to EFV occurred less frequently with the 400 mg daily dose compared to 600 mg[27].

It is possible that any changes in ENG concentrations that occur during and after the course of EFV could lead to increased incidence of adverse reactions to ENG. The most common adverse reactions leading to discontinuation of Nexplanon®/Implanon® are[7]**Error! Bookmark not defined.**:

- Bleeding irregularities (11.1%)
- Emotional lability (2.3%)
- Weight increase (2.3%)
- Headache (1.6%)
- Acne (1.3%)
- Depression (1.0%)

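### No liver test is scheduled between screening and Day 42, so no scheduled liver result can stop the 14-day efavirenz course; adding AST/ALT at Day 7 is a cheap safety improvement

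*Combined protocol and SAP*

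**What the plan says.** Section 6b lists the known EFV reactions. Under hepatotoxicity it states that "it is recommended that liver enzymes be evaluated before and during treatment with EFV", because enzymes can rise even without existing liver disease. Section 8a, the study's own risk list, repeats the point: "Additional adverse reactions to EFV include elevated liver enzymes".

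The testing schedule is in Section 4a, "Table 1: Participant Visit Schedule and Timing of Study Assessments". Its Safety Labs row is marked at Screening and on Day 42 only. Blood is also drawn on Days 2, 7, 11 and 14, but for ENG and reproductive hormones, with EFV concentrations on Days 2 and 14.

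Dosing is nightly for 14 days at 400 mg, and "The first dose of EFV will be taken in the evening of Day 1".

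Section 8b covers central nervous system effects, psychiatric effects, rash and pregnancy. On the middle two it says "They will also be counseled about the potential for psychiatric effects and rash as part of the informed consent process", and it provides study contact details for any symptom that worries the participant. It has no liver-specific step. Section 4f removes a woman who misses more than three visits, becomes pregnant, has a serious adverse event or asks to stop. Section 7d adds withdrawal, implant removal, non-compliance and emergency contraception. Neither section mentions a laboratory result.

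**The concern.** The plan cites advice to test before and during treatment. It schedules the first part and gives no reason for leaving out the second. The participants are healthy women who gain no treatment benefit from EFV, so tolerance for avoidable exposure should be low.

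An enzyme rise without symptoms would not be reported by the participant and need not become a serious adverse event. The only later panel comes four weeks after dosing has ended. By then it cannot shorten exposure, and it may miss a rise that has already settled. Section 5 also admits women with AST/ALT up to 3 times the upper limit of normal (ULN), so a participant may start EFV with values already raised.

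**Working it through.** The plan gives no figure of its own on this point. The check aligns the schedule with the dosing days.

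**Inputs.** Doses on the evenings of Days 1 to 14; visits at Screening and on Days 1, 2, 7, 11, 14, 18, 21, 25, 28, 32, 35, 39 and 42; visit window ±1 day; screening laboratory values up to 30 days before entry (Sections 4a and 5).

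**Table alignment.** The header and the Safety Labs row each have 17 columns, and the two marks fall under Screening and Day 42. As a check, the EFV row read the same way falls on Days 2 and 14, which matches the two sampling times given in the text.

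**Coverage.**
- Visits with Safety Labs: 2 of 14.
- Post-dose visits in the dosing period (Days 2, 7, 11, 14) with Safety Labs: 0 of 4.
- Last dosing day to second panel: 42 − 14 = 28 days.
- Interval between panels: from 42 − 1 = 41 days up to 41 + 30 = 71 days.

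**Doses that a test could spare.** If the result is known before the evening dose on day D, doses taken = D − 1 and doses avoidable = 14 − (D − 1) = 15 − D. The turnaround is an assumption, 0 to 2 days.

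| Draw | Same-day result | 2-day result |
|---|---|---|
| Day 6 (early end of window) | 9 | 7 |
| Day 7 | 8 | 6 |
| Day 8 (late end of window) | 7 | 5 |
| Day 11 | 4 | 2 |
| Day 14 | 1 | 0 |

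Day 7 is the useful visit. A draw there reflects only the first 6 doses and cannot show a later rise.

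**Why the stop level should take account of the screening value.** With a flat limit of 3 × ULN, a woman entering at 2.9 × ULN would be stopped by a rise of 3/2.9 − 1 = 3.4%, while one entering at 0.5 × ULN could rise 3/0.5 = 6-fold before stopping.

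**The case against.** The strongest reply is that the Section 6b sentence is background. It belongs to a list drawn from studies of EFV-based antiretroviral regimens and gives no testing interval, so it does not show that a test is required inside a 14-day, 400 mg course. That stands. A reader might infer that the protocol contradicts itself or breaks a commitment; the documents do not support this.

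Nor is liver monitoring wholly absent. Entry limits apply, alcohol is excluded, and the short course is chosen with the aim of "minimizing exposure in these healthy volunteers". Women attend in person on Days 2, 7, 11 and 14 and "will be counseled regarding when and how to inform study personnel of any potential adverse reactions". Unscheduled tests are not ruled out, and a serious adverse event leads to removal. These safeguards narrow the gap to asymptomatic rises, but none of them detects such a rise while doses remain.

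A reader might also infer a substantial liver risk. Section 8a places raised enzymes among the additional reactions, not the most common ones, and says that reactions were less frequent at 400 mg. No incidence or time course is given.

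Finally, Table 1 does not define Safety Labs. That they include AST/ALT is inferred from the screening panels in Section 4a and the limits in Section 5. If the Day 42 panel had no liver test, the gap would be wider, so the point does not depend on this reading.

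**Conclusion.** The point holds as a cheap improvement for participant safety. No scheduled liver result falls within the dosing period, and no laboratory value is a ground for stopping, although the plan itself names the risk and cites advice to test during treatment.

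The benefit is modest: about 6 of 14 doses spared (range 5 to 9) for a woman whose asymptomatic rise is visible by Day 7. That figure rests on an assumed turnaround of up to 2 days. How many women would benefit cannot be computed from the documents.

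It would be wrong to read this as a fault in the ENG pharmacokinetic analysis. Nothing in that analysis depends on the liver tests.

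**What to change.** 1. In Table 1, add AST/ALT to the existing Day 7 draw, and state that Safety Labs include AST/ALT.
2. In Section 4f, state that the Day 7 result is reviewed within about 2 days, and that EFV is stopped at a level the investigator fixes before the first dose, taking the participant's screening value into account.
3. Follow raised values until they return to about her own screening level. Returning to the entry limit is not enough, because that limit is 3 × ULN.
4. State that a woman stopped for a laboratory value alone stays in follow-up and that her ENG data are reported as a partial course. Removal for a serious adverse event stays as written.

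**Cost.** About 18 extra AST/ALT tests (one per enrolled woman) with no new visit or venipuncture, possibly a few mL beyond the planned 20 mL per visit, and prompt review of results. The study should state that it pays for repeat tests: Section 8e makes the participant responsible for the evaluation of an adverse event, while Section 11 says that she bears no costs. Any woman stopped early may lose the full two-week ENG comparison that is the primary outcome. The margin is small: 18 − 15 = 3 women, and the assumed 20% drop-out (18 × 0.2 = 3.6) already uses it. This loss arises only if a woman reaches the stop level.
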